16.1 Adverse Events

An AE is defined as any untoward medical occurrence associated with the use of an IP in humans, whether or not considered IP-related. An AE can be any unfavorable and unintended sign (e.g., an abnormal laboratory finding), symptom, or disease temporally associated with the use of an IP, without any judgment about causality. An AE can arise from any use of the IP (e.g., off-label use, use in combination with another drug or medical device) and from any route of administration, formulation, or dose, including an overdose. An AE can arise from any delivery, implantation, or use of a medical device, including medical device failure, subject characteristics that may impact medical device performance (e.g., anatomical limitations), and therapeutic parameters (e.g., energy applied, sizing, dose release, and anatomic fit) associated with medical device use.

All AEs spontaneously reported by the subject and/or in response to an open question from study personnel or revealed by observation, physical examination or other diagnostic procedures will be recorded in the source document and on the appropriate pages of the case report form. Any clinically relevant deterioration in clinical finding is considered an AE and must be recorded. When possible, signs and symptoms indicating a common underlying pathology should be noted as one comprehensive event.

Documentation regarding the AE should be made as to the nature, date of onset, end date, severity, and relationship to IP, action(s) taken, seriousness, and outcome of any sign or symptom observed by the physician or reported by the subject upon indirect questioning.

Severity of an AE is defined as a qualitative assessment of the degree of intensity of an AE as determined by the investigator or reported to him/her by the subject. The assessment of severity is made irrespective of relationship to IP or seriousness of the event and should be evaluated according to the following scale:

- Mild: Event is noticeable to the subject, but is easily tolerated and does not interfere with the subject's daily activities.
- Moderate: Event is bothersome, possibly requiring additional therapy, and may interfere with the subject's daily activities.
- Severe: Event is intolerable, necessitates additional therapy or alteration of therapy, and interferes with the subject's daily activities.

A determination will be made of the relationship (if any) between an adverse event and the study drug or study procedure, as applicable. A causal relationship is present if a determination is made that

there is a reasonable possibility that the adverse event may have been caused by the drug or study procedure.

The relationship of each AE to the IP should be determined by the investigator using these explanations:

- **Suspected:** A reasonable possibility exists that the IP caused the AE. A suspected AE can be further defined as:
 - **Definite:** Relationship exists when the AE follows a reasonable sequence from the time of IP administration, follows a known response pattern of the drug class, is confirmed by improvement on stopping the IP and no other reasonable cause exists.
 - **Probable:** Relationship exists when the AE follows a reasonable sequence from the time of IP administration, follows a known response pattern of the drug class, is confirmed by improvement on stopping the IP and the suspect IP is the most likely of all causes.
 - **Possible:** Relationship exists when the AE follows a reasonable sequence from the time of IP administration, but could also have been produced by the subject's clinical state or by other drugs administered to the subject.
- **Not Suspected:** A reasonable possibility does not exist that the IP caused the AE.
 - **Not Related:** Concurrent illness, concurrent medication, or other known cause is clearly responsible for the AE, the administration of the IP and the occurrence of the AE are not reasonably related in time, OR exposure to IP has not occurred.

The expectedness of an AE should be determined based upon existing safety information about the IP using these explanations:

- **Unexpected:** An AE that is not listed in the Investigator's Brochure (IB) or is not listed at the specificity or severity that has been observed.
- **Expected:** An AE that is listed in the IB at the specificity and severity that has been observed.
- **Not applicable:** An AE unrelated to the IP.

AE events that are mentioned in the IB as occurring with a class of products or as anticipated from the pharmacological/mechanical (or other) properties of the product, but are not specifically mentioned as occurring with the particular product under investigation are to be considered unexpected.

The investigator should initially classify the expectedness of an AE, but the final classification is subject to the Medical Monitor's determination.

An AE is considered serious if, in the view of either the investigator or sponsor, it results in any of the following outcomes:

- Death;
- A life-threatening AE;

Note: An AE is considered "life-threatening" if, in the view of either the investigator or sponsor, its occurrence places the subject at immediate risk of death. It does not include an AE that, had it occurred in a more severe form, might have caused death.

The AE reporting period ends upon study exit. Study drug includes the investigational drug under evaluation and vehicle given during any stage of the study. All AEs will be coded using the MedDRA 21.0.

Treatment-emergent adverse events (TEAEs) are defined as any adverse event that occurs or worsens after the first dose of study treatment. AEs recorded in the eCRF which began prior to treatment will not be included in the summary tables but will be included in the AE data listings.

An overall summary will be presented that includes the number of AEs, TEAEs, serious AEs (SAE), and serious TEAEs (TE-SAE). The summary will also include the number and percentage of subjects withdrawn due to an AE, the number and percentage of subjects with an AE resulting in death, and the number and percentage of subjects who experienced at least one AE, TEAE, SAE and TE-SAE, by treatment group and for all subjects. This summary will include breakdowns of AEs further categorized as ocular or non-ocular. The summary will also include the number and percentage of resolved ocular AEs, and the mean number of days until AE resolution for resolved ocular AEs.

Additional summaries of TEAEs will be provided showing the number and percentage of subjects who experienced at least one TEAE. These summaries will be presented by SOC and PT. Non-ocular TEAEs will be summarized using discrete summary statistics and presented by treatment group at the subject and event level by SOC and PT. Ocular TEAEs will be similarly summarized at the subject and event level as well as for study and fellow eyes separately. If a subject reports the same PT multiple times within the same SOC, that PT will only be reported once within that SOC. As with the PT, if a subject reports multiple conditions within the same SOC, that SOC will only be reported once. In the summary, SOC will be listed in order of descending frequency for all subjects; PTs will be listed in order of descending frequency for all subjects within each SOC. The occurrence of non-ocular and ocular TEAEs will also be tabulated by SOC, PT, and maximal severity, as well as by study day of onset (prior to Day 15, Day 15 to Day 43, After Day 43).

Separate summaries will be provided for the following categories of AEs:

- Ocular TEAEs
- Non-ocular TEAEs
- Treatment-related ocular TEAEs
- Treatment-related non-ocular TEAEs
- SAEs

Summaries of TEAEs by maximal severity will be presented for ocular AEs and non-ocular AEs separately. The number of subjects with any TEAEs (along with percentages) will be tabulated by SOC and PT within each SOC by treatment group. To count the number of subjects with any TEAEs, if a subject has multiple TEAEs coded to the same PT within the same SOC, the subject will be counted once under the maximal severity.

All TEAEs with possible, probable, and definite relationship to IP are considered as treatment-related TEAEs.

All AEs will be presented in a subject listing that classifies each AE as ocular or non-ocular and indicates whether it is a TEAE. Separate listings will be produced for AEs leading to study discontinuation, AEs leading to death and SAEs.

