11 ADVERSE EVENTS

11.1 Adverse Event

An AE is defined as any untoward medical occurrence associated with the use of an IP in humans, whether or not considered IP-related. An AE can be any unfavorable and unintended sign (e.g., an abnormal laboratory finding), symptom, or disease temporally associated with the use of an IP, without any judgment about causality. An AE can arise from any use of the IP (e.g., off-label use, use in combination with another drug or medical device) and from any route of administration, formulation, or dose, including an overdose. An AE can arise from any delivery, implantation, or use of a medical device, including medical device failure, subject characteristics that may impact medical device performance (e.g., anatomical limitations), and therapeutic parameters (e.g., energy applied, sizing, dose release, and anatomic fit) associated with medical device use.

All AEs spontaneously reported by the subject and/or in response to an open question from study personnel or revealed by observation, physical examination or other diagnostic procedures will be recorded in the source document and on the appropriate pages of the CRF. Any clinically relevant deterioration in clinical finding is considered an AE and must be recorded. When possible, signs and symptoms indicating a common underlying pathology should be noted as one comprehensive event.

Documentation regarding the AE should be made as to the nature, date of onset, end date, severity, and relationship to IP, action(s) taken, seriousness, and outcome of any sign or symptom observed by the physician or reported by the subject upon indirect questioning.

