TABLE 14.2.18.3.3	SYMPTOM ASSESSMENT IN DRY EYE (SANDE) STRATIFIED BY TIME TO CAE QUALIFICATION – COMBINED STAGE 1 AND STAGE 2	MITT POPULATION WITH OBSERVED DATA ONLY
TABLE 14.2.19.1.1	RESPONDER ANALYSIS – STAGE 1	MITT POPULATION WITH OBSERVED DATA ONLY
TABLE 14.2.19.1.2	RESPONDER ANALYSIS – STAGE 2	MITT POPULATION WITH OBSERVED DATA ONLY
TABLE 14.2.19.1.3	RESPONDER ANALYSIS – COMBINED STAGE 1 AND STAGE 2	MITT POPULATION WITH OBSERVED DATA ONLY

Table Number	Title	Population
TABLE 14.2.20.1.1	RESPONDER SHIFT FROM BASELINE – STAGE 1	MITT POPULATION WITH OBSERVED DATA ONLY
TABLE 14.2.20.1.2	RESPONDER SHIFT FROM BASELINE – STAGE 2	MITT POPULATION WITH OBSERVED DATA ONLY
TABLE 14.2.20.1.3	RESPONDER SHIFT FROM BASELINE – COMBINED STAGE 1 AND STAGE 2	MITT POPULATION WITH OBSERVED DATA ONLY
TABLE 14.2.21.1.1	P-VALUE SUMMARY – STAGE 1	MITT POPULATION WITH OBSERVED DATA ONLY
TABLE 14.2.21.1.2	P-VALUE SUMMARY – STAGE 2	MITT POPULATION WITH OBSERVED DATA ONLY
TABLE 14.2.21.1.3	P-VALUE SUMMARY – COMBINED STAGE 1 AND STAGE 2	MITT POPULATION WITH OBSERVED DATA ONLY
TABLE 14.3.1.1.1	ADVERSE EVENT SUMMARY – STAGE 1	SAFETY POPULATION
TABLE 14.3.1.1.2	ADVERSE EVENT SUMMARY – STAGE 2	SAFETY POPULATION
TABLE 14.3.1.1.3	ADVERSE EVENT SUMMARY – COMBINED STAGE 1 AND STAGE 2	SAFETY POPULATION
TABLE 14.3.1.2.1	ALL OCULAR ADVERSE EVENTS	SAFETY POPULATION
TABLE 14.3.1.2.2	ALL OCULAR ADVERSE EVENTS – STAGE 2	SAFETY POPULATION
TABLE 14.3.1.2.3	ALL OCULAR ADVERSE EVENTS – COMBINED STAGE 1 AND STAGE 2	SAFETY POPULATION
TABLE 14.3.1.3.1	ALL NON-OCULAR ADVERSE EVENTS – STAGE 1	SAFETY POPULATION
TABLE 14.3.1.3.2	ALL NON-OCULAR ADVERSE EVENTS – STAGE 2	SAFETY POPULATION
TABLE 14.3.1.3.3	ALL NON-OCULAR ADVERSE EVENTS – COMBINED STAGE 1 AND STAGE 2	SAFETY POPULATION
TABLE 14.3.1.4.1	ALL OCULAR TREATMENT-EMERGENT ADVERSE EVENTS – STAGE 1	SAFETY POPULATION
TABLE 14.3.1.4.2	ALL OCULAR TREATMENT-EMERGENT ADVERSE EVENTS – STAGE 2	SAFETY POPULATION
TABLE 14.3.1.4.3	ALL OCULAR TREATMENT-EMERGENT ADVERSE EVENTS – COMBINED STAGE 1 AND STAGE 2	SAFETY POPULATION
TABLE 14.3.1.5.1	ALL NON-OCULAR TREATMENT-EMERGENT ADVERSE EVENTS – STAGE 1	SAFETY POPULATION
TABLE 14.3.1.5.2	ALL NON-OCULAR TREATMENT-EMERGENT ADVERSE EVENTS – STAGE 2	SAFETY POPULATION
TABLE 14.3.1.5.3	ALL NON-OCULAR TREATMENT-EMERGENT ADVERSE EVENTS – COMBINED STAGE 1 AND STAGE 2	SAFETY POPULATION
TABLE 14.3.1.6.1	ALL OCULAR TREATMENT-RELATED TREATMENT-EMERGENT ADVERSE EVENTS – STAGE 1	SAFETY POPULATION

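### SAP 16.1 counts an AE that worsens after first dose as treatment-emergent, then bars AEs that began before treatment from the summary tables with no exception for worsening

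*SAP*

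**What the plan says.** SAP Section 16.1 sets out the definition: "Treatment-emergent adverse events (TEAEs) are defined as any adverse event that occurs or worsens after the first dose of study treatment". The sentence after it says: "AEs recorded in the eCRF which began prior to treatment will not be included in the summary tables", and continues "but will be included in the AE data listings". No exception is made for an event that worsens.

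The same section plans an overall summary that counts AEs separately from TEAEs, TEAE summaries by system organ class and preferred term, and breakdowns by relatedness, maximal severity and day of onset. On the listing it says: "All AEs will be presented in a subject listing that classifies each AE as ocular or non-ocular and indicates whether it is a TEAE". The table index in SAP Section 20 adds all-AE tables beside the TEAE tables, for example "ALL OCULAR ADVERSE EVENTS – COMBINED STAGE 1 AND STAGE 2".

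Protocol Section 12.4.7 asks for the incidence of every TEAE and contains no exclusion by onset date. On recording, Protocol Section 11.1 (repeated in SAP 16.1) says: "Any clinically relevant deterioration in clinical finding is considered an AE and must be recorded".

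**The concern.** An AE that starts before treatment and becomes worse on it meets the TEAE definition and is also caught by the exclusion. A programmer following the text has to break one of the two rules, and nothing says which one gives way.

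The window in which this can happen exists for every randomised patient. AEs are queried at Visit 1 after a 90-minute chamber exposure, and again at Visit 2 after two weeks of vehicle run-in (Protocol Sections 10.3.1.1 and 10.3.1.2). In a dry-eye population, worsening of an ocular complaint that was already present is a relevant tolerability signal.

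Safety and tolerability are part of the primary objective of both stages. The Stage 1 tables form the interim output (SAP Section 20), and dose groups may be terminated for safety or tolerability at that point (SAP Section 17). Which events enter the TEAE tables should therefore not depend on a programmer's choice.

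**Working it through.** The plan states no figure on this point and no arithmetic applies, so the check is a comparison of texts. Whether an event that worsened is lost turns on three questions.

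**Which rule governs?** SAP 16.1 does not say. The exclusion refers to the summary tables without qualification. Other parts of the SAP do not follow it: the overall summary (14.3.1.1.x) counts AEs apart from TEAEs, and the all-AE tables (14.3.1.2.x ocular, 14.3.1.3.x non-ocular) would largely duplicate the TEAE tables (14.3.1.4.x, 14.3.1.5.x) unless they hold AEs that are not TEAEs. The protocol does not settle it either: SAP Section 1 says its methods supersede the protocol's, while SAP Section 18 declares no changes from the protocol. If applied, the exclusion is an undeclared departure from Protocol 12.4.7.

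**When does treatment start?** SAP 8.3 usually puts baseline, the last measure before treatment, at Day 1. SAP 12.1 and 12.2 count compliance and exposure from Visit 2. All three favour Day 1. SAP 16.1, however, counts vehicle as study drug whatever the stage at which it is given, and Protocol Appendix 1 shows run-in vehicle instilled at Visit 1.

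**Where is a worsening recorded?** Protocol 11.1 makes a deterioration an AE but does not say whether it receives its own record. It also asks for related signs and symptoms to be grouped as one event where possible. The items to be documented include onset date, end date and severity, but no date of worsening.

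The combinations for an AE that begins in the run-in and worsens after Day 1 are:

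| Rule applied | Start of treatment | Recording of the worsening | Result |
|---|---|---|---|
| Exclusion, literally | Day 1 | Original record, onset unchanged | A TEAE by definition, but absent from the TEAE tables; listed only |
| TEAE definition and table index | Day 1 | Either | In the TEAE tables |
| Either | Day 1 | New record, post-dose onset | In the TEAE tables |
| Either | First run-in drop | Either | Already a TEAE if it began after that drop; not excluded |

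Only the first row loses the event. There it is missing from 14.3.1.4.x and 14.3.1.5.x (TEAEs), 14.3.1.6.x and 14.3.1.7.x (treatment-related), 14.3.1.9.x and 14.3.1.10.x (maximal severity) and 14.3.1.11.x and 14.3.1.12.x (day of onset). The TEAE count in 14.3.1.1.x is also affected if the exclusion reaches that table. The listing could still flag the event as a TEAE, so listing and tables would not reconcile.

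The last row avoids the loss but makes AEs that began on run-in vehicle count as TEAEs of the arm assigned later. The text thus supports materially different TEAE counts from the same data.

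**The case against.** The strongest reply is that the second sentence was meant only for AEs that are not TEAEs. The separate AE and TEAE counts, the all-AE tables and the TEAE flag in the listing fit that reading. A deterioration must be recorded as an AE, and if it is entered as a new one it has a post-dose onset and is tabulated. Tolerability also does not rest on the AE tables alone: drop comfort is summarised by arm (SAP 16.2), slit-lamp shift tables compare follow-up visits with Visit 1 before the chamber (SAP 16.4), withdrawals due to AEs are counted, and the data review committee sees all available safety data.

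Much of this stands. A reader might infer that run-in events that worsen on drug are certain to disappear from the safety tables. The documents do not support that: it takes the first row of the table above, and the event stays in the listing even then. A reader might also infer that the omission favours the active arms. That holds only if AXR-159 worsens existing complaints more often than vehicle does. The documents do not describe it as irritating, and the protocol synopsis reports that the eye drop was very well tolerated in preclinical species.

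The conflict between the two sentences is not removed. The intended reading has to be guessed, the recording rule is not written down, and the all-AE tables add a further conflict with the exclusion as worded.

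**Conclusion.** SAP 16.1 contradicts itself for AEs that begin before treatment and worsen after it. An actual omission from the TEAE tables depends on three conditions together: the exclusion is applied literally, treatment is taken to start on Day 1, and the worsening is kept on the original record. The second is the likelier reading of the SAP; the other two are open.

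The size cannot be estimated, because the documents give no rate of AEs ongoing at Day 1 and no rate of worsening. Purely as an assumption, if 5% to 15% of patients had such an ocular AE and 10% to 30% of these worsened, the share would be 0.05 × 0.10 = 0.5% to 0.15 × 0.30 = 4.5%. In a combined active arm of 113 that is 0.6 to 5.1 patients. A reader might take this as an estimate, but neither percentage has support in the documents, and the calculation treats every worsening as lost.

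The point concerns the rule that fills the TEAE outputs. It leaves the efficacy analyses, alpha and sample size unchanged. It should be settled before the treatment codes are opened.

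**What to change.** Replace the exclusion sentence in SAP 16.1 with a rule to this effect: AEs that began before the first randomised dose and did not increase in severity or seriousness afterwards are not TEAEs and stay out of the TEAE summaries; AEs that did worsen are TEAEs, summarised at their post-dose severity with the date of worsening as onset. Apply it to tables 14.3.1.1.x and 14.3.1.4.x to 14.3.1.12.x.

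Add three statements:

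- Run-in vehicle is not study treatment for the purpose of defining TEAEs.
- A worsening is entered as a new AE record with its own onset date, or the date of the severity change is captured.
- The AE counts in 14.3.1.1.x and the all-AE tables 14.3.1.2.x and 14.3.1.3.x include pre-treatment AEs.

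The cost is a small data-entry convention and a programming flag. The recording rule is needed as well as the SAP wording: if a site has overwritten the severity on an existing record without a date, a flag alone cannot recover when the event worsened.

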Summary of Visit Schedule:	5 visits over the course of approximately 14 weeks 
• Visit 1 = Screening (Day -14 ± 2)• Visit 2 = Baseline & Randomization, Day 1• Visit 3 = 2-Week Follow-Up (Day 15 ± 2)• Visit 4 = 1.5 Month Follow-up (Day 43 ± 2)• Visit 5 = 3 Month Follow-up (Day 85 ± 2)
Measures Taken to Reduce Bias:	This is a randomized treatment assignment, double-masked study
Study Population Characteristics:	
Number of Subjects:	
Stage 1:
 
The total number of randomized patients for Stage 1 of the study will be approximately 100 at up to 2 sites. Approximately 50% of patients should have a baseline eye dryness score of ≥ 60 and approximately 50% of patients should have a baseline inferior corneal staining score (ICCS) > 1.5 according to the Ora Calibra® staining scale. Based upon data from Xiidra®, OPUS 2 a screen failure rate of $\sim 50\%$ is expected. Thus, ~ 200 patients will need to be screened to achieve ~ 100 patients randomized to treatment.
 
Stage 2:
 
The total number of randomized patients for Stage 2 of the study will be approximately 330 (see Figure 6.1-1, Stage 2) at up to 7 sites. Approximately 50% of patients should have a baseline eye dryness score of ≥ 60 and approximately 50% of patients should have a baseline inferior corneal staining score (ICCS) > 1.5. Based upon data from Xiidra®, OPUS 2 a screen failure rate of $\sim 50\%$ is expected. Thus, ~ 660 patients will need to be screened to achieve ~ 330 patients randomized to treatment.
 
Note: patients can be reallocated from discontinued groups to increase the power in groups that are continued at the discretion of the DRC.

Condition/Disease:	Dry Eye Disease (DED)

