expansion of the AXR-159 Ophthalmic Solution 50 mg/mL and vehicle TID groups (N = 45 per group) and to halt the initiation of Stage 1, Cohorts 2 and 3. If AXR-159 Ophthalmic Solution 50 mg/mL TID is NOT safe and well tolerated the DRC will recommend Stage 1, Cohort 2 (8 patients on AXR-159 Ophthalmic Solution 30 mg/mL TID and 2 patients on vehicle TID) and to halt the Cohort 1 Expansion Cohort. Patients already enrolled in Stage 1, Cohort 1 will continue at the investigator's discretion. Any patients that discontinue during the study will be followed through the resolution of their adverse event(s) or end of study. When the 10th patient enrolled in Stage 1, Cohort 2 completes the Week 2 visit, a DRC will evaluate all available safety data. If AXR-159 Ophthalmic Solution 30 mg/mL TID is safe and well tolerated the DRC will recommend expansion of the AXR-159 Ophthalmic Solution 30 mg/mL and vehicle TID Expansion Cohort (N = 40 per group) and to halt Cohort 3. If AXR-159 Ophthalmic Solution 30 mg/mL TID is NOT safe and well tolerated the DRC will recommend Stage 1, Cohort 3 (8 patients on AXR-159 Ophthalmic Solution 30 mg/mL BID and 2 patients on vehicle BID) and to halt the Cohort 2 Expansion Cohort. Patients already enrolled in Stage 1, Cohort 2 will continue at the investigator's discretion. When the 10th patient enrolled in Stage 1, Cohort 3 completes the Week 2 visit, a DRC will evaluate all available safety data. If AXR-159 Ophthalmic Solution 30 mg/mL BID is safe and well tolerated the DRC will recommend expansion of the AXR-159 Ophthalmic Solution 30 mg/mL and vehicle BID Expansion Cohort (N = 35 per group). If AXR-159 Ophthalmic Solution 30 mg/mL BID is NOT safe and well tolerated the DRC will recommend stopping the study. Thus, in stage 1 a successive cohort will only be started if the previous cohort is felt to be either unsafe or poorly tolerated by the DRC.

When the last patient enrolled in Stage 1 completes the Month 3 visit in the Expansion Cohort, a formal Interim Analysis will be completed and the DRC will evaluate all available safety and efficacy data from Stage 1 before recommending initiation of Stage 2. Stage 2 is a parallel group design and the DRC may recommend up to a maximum of 7 groups as depicted in [Figure 6.1-1](#). Groups that are either unsafe, poorly tolerated, or likely futile may be discontinued by the DRC. The DRC may reallocate patients to the surviving AXR-159 Ophthalmic Solution dose groups.

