11.5 Type and Duration of the Follow-up of Subjects after Adverse Events

Any serious adverse event occurring during the study period (beginning with informed consent) and for at least 12 weeks after the last dose of study drug must be immediately reported, but no later than 24 hours after learning of a serious adverse event. Serious adverse events must be reported to AxeroVision Inc. (or Agent of AxeroVision Inc.) as listed on the AxeroVision Inc. Study Contacts Sheet and recorded on the serious adverse event form. All patients with a serious adverse event must be followed up and the outcomes reported. The investigator must supply AxeroVision Inc. and the IRB/IEC with any additional requested information (e.g., autopsy reports and discharge summaries).

In the event of a serious adverse event, the investigator must:

1. Notify AxeroVision Inc. immediately by fax or email using the serious adverse event form (contact details can be found on page 1 of the serious adverse event form); phone numbers and relevant AxeroVision Inc. personnel contacts are also on the front page of the protocol.
2. Obtain and maintain in his/her files all pertinent medical records, information, and medical judgments from colleagues who assisted in the treatment and follow-up of the patient.
3. Provide AxeroVision Inc. with a complete, written description of the adverse event(s) on the serious adverse event form describing the event chronologically, including any treatment given (e.g., medications administered, procedures performed) for the adverse event(s). Summarize relevant clinical information about the event: signs, symptoms, diagnosis, clinical course and relevant clinical laboratory tests, etc. Include any additional or alternative explanation(s) for the causality which includes a statement as to whether the event was or was not related to the use of the investigational drug.

4. Promptly inform the governing IRB/IEC of the serious adverse event as required by the IRB/IEC, local regulations, and the governing health authorities.

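### The only AE-duration figure is a mean over resolved ocular AEs; it runs low, and lower in the slower arm when AEs last weeks or start late

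*SAP*

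**What the plan says.** SAP 16.1 (Adverse Events) sets out an overall AE summary by treatment group. On resolution it gives two items in one sentence. The first is a count: "The summary will also include the number and percentage of resolved ocular AEs". The second is a duration: "the mean number of days until AE resolution for resolved ocular AEs". The same section states: "The AE reporting period ends upon study exit".

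Scheduled treatment runs from Day 1 to Visit 5 at Day 85 ± 2 (Protocol synopsis, Summary of Visit Schedule), so an AE can be observed for at most about 84 days.

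Four other provisions bear on the point:
- For each AE the record covers "nature, date of onset, end date, severity, and relationship to IP, action(s) taken, seriousness, and outcome" (SAP 16.1).
- "All AEs will be presented in a subject listing that classifies each AE as ocular or non-ocular" (SAP 16.1).
- Protocol 6.1 has a follow-up rule: "Any patients that discontinue during the study will be followed through the resolution of their adverse event(s) or end of study".
- Protocol 11.5 sets a longer window for serious AEs only. An SAE occurring during the study and "for at least 12 weeks after the last dose of study drug must be immediately reported".

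The SAP has no censored time-to-resolution analysis and no rule for an AE that is still ongoing at exit.

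**The concern.** Time to resolution is right-censored at the end of observation. Averaging only the AEs seen to resolve conditions on the event being short relative to the follow-up left after its onset. The longer an arm's AEs last, the more of them drop out of its mean, so the error differs between arms and pulls them together.

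Tolerability is among the primary objectives of both stages (SAP 2), and this is the only AE-duration figure in the SAP. It belongs to the overall AE summary, planned as Table 14.3.1.1.1 for Stage 1. SAP 20 sends Stage 1 tables to the interim analysis, after which SAP 17 allows individual dose groups to be terminated for tolerability. A duration contrast that is too small could therefore be in front of the committee at that point.

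**Working it through.** Neither document states an AE duration or resolution rate, so there is no planned figure to reproduce. The check asks what the statistic would report for given true durations.

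**Inputs**
- From the documents: T = 84 days (Day 1 to Day 85); reporting ends at exit; the mean is taken over resolved AEs only.
- Assumed: duration D exponential with mean m; onset uniform over 0 to 84 days; all patients followed to day 84; no end dates collected after exit.

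**Formulas**
- Share resolved: p = 1 − (m/T)(1 − e^(−T/m)).
- Contribution of resolved AEs: N = m − 2m²/T + (m/T)·e^(−T/m)·(T + 2m). This is m − (u + m)e^(−u/m) averaged over remaining follow-up u from 0 to T.
- Reported mean: N/p.

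**Two cases in full**
- m = 20: e^(−4.2) = 0.0150; p = 1 − (20/84)(0.9850) = 0.765; N = 20 − 9.524 + 0.443 = 10.919; reported mean 10.919/0.765 = 14.3 days.
- m = 40: e^(−2.1) = 0.1225; p = 1 − (40/84)(0.8775) = 0.582; N = 40 − 38.095 + 9.563 = 11.468; reported mean 11.468/0.582 = 19.7 days.

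| True mean (days) | Share resolved | Reported mean (days) |
|---|---|---|
| 5 | 94% | 4.7 |
| 7 | 92% | 6.4 |
| 10 | 88% | 8.7 |
| 14 | 83% | 11.2 |
| 20 | 77% | 14.3 |
| 28 | 68% | 17.1 |
| 40 | 58% | 19.7 |
| 56 | 48% | 21.8 |

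**Contrasts between arms**
- 20 against 40 days: a true gap of 20 days shows as 19.7 − 14.3 = 5.4 days, and a twofold ratio as 19.7/14.3 = 1.38.
- 28 against 56 days: twofold shows as 21.8/17.1 = 1.27.
- 5 against 10 days: twofold shows as 8.7/4.7 = 1.85, so little is lost.

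**Sensitivity to the assumptions**
- Lognormal durations (log SD 1), uniform onset: 20 and 40 days show as 13.3 and 20.1.
- Early onset (exponential with mean 14 days, truncated at 84): 20 and 40 days show as 17.6 and 25.4. The bias is smaller but in the same direction.
- The percentage resolved depends on onset as well as duration. A true mean of 40 days gives 58% resolved with uniform onset and about 82% with early onset.

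**Does a censored estimate repair it?** With unresolved AEs censored at exit, the simulated Kaplan-Meier medians for true means of 20 and 40 days are 13.9 and 27.7. The true medians are 20·ln 2 = 13.9 and 40·ln 2 = 27.7. The twofold ratio is recovered.

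**The case against.** The case on the other side is substantial.

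- **Nothing is hidden.** The same sentence reports the number and percentage resolved, every AE is listed, and the statistic is labelled as applying to resolved AEs. This stands. In the 20 against 40 example, 77% against 58% resolved would alert a careful reader. But that percentage mixes duration with onset timing, and it does not tell the reader how far to correct the mean. Listings are not a summary by arm.
- **The size is assumed.** No durations are given, and short ocular AEs would hardly be affected. This stands, and it limits the point to AEs that last several weeks or start late.
- **Little depends on the figure.** No test or decision rule is attached. Protocol Table 4-1 lists TEAE incidence and shift tables, not AE duration, and SAP 8.5 calls all efficacy analyses exploratory. This stands and sets the level at minor.
- **The cut at exit is partly inferred.** Ending the reporting period does not say whether end dates of ongoing AEs are still collected, and Protocol 6.1 follows patients who discontinue to resolution or end of study. This stands. Taking no later end dates is the worst case on this point, and the conflict between the two provisions itself needs settling.
- **Kaplan-Meier has its own difficulties.** Patients needing rescue are exited (Protocol 10.2.2) and AEs are a reason for discontinuation (Protocol 10.6.2), so censoring may be informative. One subject may contribute several AEs or both eyes. Both limits belong with the table. Neither favours the mean over resolved AEs, which faces the same exits and also discards the unresolved AEs.

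**Conclusion.** The point holds as a minor one. The mean over resolved ocular AEs is biased low, and the bias grows with true duration. Under exponential durations, uniform onset over 84 days and no end dates after exit, it is 29% low at a true 20 days (1 − 14.3/20) and 51% low at 40 days (1 − 19.7/40). A 20-day difference then shows as 5.4 days. For AEs of about a week it is about 9% low (1 − 6.4/7). The direction does not depend on the assumed distribution; the size does.

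A reader might infer three stronger things, and the documents support none of them:
- That long-lasting AEs go unreported. They are missing from one mean, not from the counts or listings.
- That a slow arm will generally look close to a fast one. This needs durations that are long relative to the remaining follow-up, and neither document says they are.
- That this is the only time-based tolerability figure. TEAEs are also tabulated by day of onset (SAP 16.1), and drop comfort is scored at instillation and at 1 and 2 minutes, with a questionnaire at 3 minutes (SAP 16.2). It is the only AE-duration figure.

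**What to change.** In SAP 16.1:
1. Report, by arm, the Kaplan-Meier median time to resolution of ocular TEAEs, with unresolved AEs censored at last contact. Where the curve does not fall to one half, report the median as not reached.
2. Keep the number and percentage resolved, and show the number unresolved beside them.
3. State the censoring date and whether end dates after exit are collected, so that SAP 16.1 (reporting ends at exit) and Protocol 6.1 (follow-up to resolution or end of study) agree.
4. If the mean is kept, label it as conditional on resolution.
5. Make any confidence interval allow for several AEs or both eyes per subject, for example by resampling subjects. Add a note that exit for rescue or AEs may make the censoring informative.

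Onset date, end date and outcome are already recorded, so the analysis needs no new kind of data. The cost is SAP wording and one extra table for each of Stage 1, Stage 2 and the combined data. Reported durations will look longer than under the present definition.
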